**Table 1. Study Summary**

§Sample Size	N = 424 (50/50 by randomization strata)
Population	1. Lung transplantation (N = 200) 2. Heart Transplantation / LVAD implantation (N = 224)
Rationale	
 
• Comparison of iNO and iEpo impact on outcomes – evaluate for equivalency
 
• PVD therapy indications:               
 
1. Lung Transplant: Improvement of ventilator and perfusion matching after lung allograft implantation by vasodilation of ventilated pulmonary capillaries
 
2. Heart Transplant/LVAD Implantation: Improvement of RV contractility after cardiac allograft implantation or LVAD implantation by PVR reduction
 
 
 

Study Design	Prospective, Randomized, Double-Blinded
Primary Outcomes	1. Lung Transplant: Severe PGD (grade 3) 2a. Heart Transplant: RVAD insertion b. LVAD: INTERMACS Moderate or Severe RVF
Secondary Outcomes	All populations: 
 
• ICU LOS (days)
 
• Hospital LOS (days)
 
• Mechanical ventilator duration (hours)
 
• Postoperative AKI
 
• In-hospital mortality
 
• Mortality 30-day, 90-day, 1-year
 

Study length*	24-36 months

§Sample size powered for primary outcomes

\*Study length is determined through sample size divided by annual operations at Duke University Hospital; AKI = Acute kidney injury; iEpo = inhaled epoprostenol; iNO = Inhaled nitric oxide; ICU = Intensive care unit; LOS = Length of stay; LVAD = Left ventricular assist device; PGD = Primary graft dysfunction; PVD = Pulmonary vasodilators; PVR = Pulmonary vascular resistance; RVF = Right ventricular failure

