### 4. Design & Procedures:

#### Aim I – Development of a Definitive Clinical Trial Investigation.

**1. Randomization and Double-Blinding.** The clinical research unit (CRU) will receive preoperative notification of lung and heart transplantation patients by reviewing the transplant waitlist. Preoperative notification of LVAD implantation will be done by the review of the cardiothoracic surgical schedule. Using a 50% randomization process utilized and established by the CRU at Duke University Hospital, each eligible patient will be randomized to receive either iNO or iEPO. The primary endpoint data will be collected and documented in an electronic data capture system during the period of time the patient, clinical care team, and study team are blinded. Primary endpoint data collection will be complete prior to the subjects' discharge from the ICU, at which point the unblinding will occur. Since primary endpoint data collection will occur during the blinded period, the potential for bias will be substantially minimized.

**2. Measured Outcomes.** The primary endpoint for the comparison of efficacy in the Lung Transplant population will be the incidence of Grade 3 Primary Graft Dysfunction (PGD). This is defined by the International Society of Heart and Lung Transplantation (ISHLT) as severe hypoxemia with a PaO2-to-FiO2 ratio < 200 or the presence of venovenous extracorporeal membrane oxygenation (VV ECMO) at a time-point within the first 72

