## Research Summary – Inhaled Pulmonary Vasodilators in Thoracic Transplantation & LVAD Surgery

hours after lung transplantation. The primary endpoint for the comparison of efficacy in LVAD patients will be incidence of moderate or severe RV failure according to Interagency Registry for Mechanically Assisted Circulatory Support (INTERMACS) scoring. The primary endpoint for the comparison of efficacy in the heart transplant subset will be the incidence rate of RVAD insertion. Secondary endpoints related to clinical outcomes for all populations will be duration of postoperative mechanical ventilation, ICU Length of Stay (LOS), hospital LOS, incidence of acute kidney injury, incidence of in-hospital mortality, as well as postoperative mortality at 30-days, 90-days, and 1-year after operation (Table 1).

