**11. Data Analysis & Statistical Considerations:** Summary statistics will be computed for demographic, clinical, and outcome variables in the form of frequencies (percentage) for categorical variables and mean (standard deviation) for continuous variables for each arm. Univariate analysis will be performed to compare the difference of each variable between treatment groups by chi-square or Fisher exact tests for categorical variables, and t-tests or Wilcoxon Rank-Sum tests for continuous variables depending on data normality. The univariate results for the outcome variables will provide information on iNO treatment effect in comparison to iEPO without taking into account other potential confounding factors. All non-outcome variables meeting  $p < 0.15$  association with treatment group will be considered for variable selection to build a multivariable regression model. For each outcome of interest, we will start with a regression model (logistic regression for binary outcomes or generalized linear model for continuous outcomes) with all variables selected from univariate analysis described above. Based on stepwise variable selection, we will determine the final set of covariates to be included in the final multivariable model to test the treatment group effect. Based on the analysis results, we will be able to understand if iNO is equivalent to iEPO (no significant difference) or significantly better or worse than iEPO (significant treatment effect) to address the efficacy of iNO for Aim 1. Several of secondary measures will be obtained over time. We will apply generalized mixed model to take into account the repeated measures over time to test for treatment effect. In the case of patients have switched to the other arm due to clinical decision, we will conduct the primary analysis based on the intent to treat (ITT) without reclassifying treatment assignment. In addition, protocol analysis, where only patients follow the protocol assignment are included will also be conducted to verify ITT results. For Aim 2 to compare cost capture analysis, the comparison of cost measures between two groups will be tested by two sample t-test.

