Based on recent *annual* operations, approximately 120 LVAD implantations, 60 heart transplantations, and 110 Lung transplantations were performed at Duke University Hospital during FY 2014 – 2015. This study has been individually powered to primary endpoints for each arm (Table 1) and the duration of study enrollment has been determined according to annual operations and sample-size calculations. We estimated sample size based on equivalence test of the incidence rates of a binary outcome (e.g. PGD grade 3 (PGD-3)) of two treatment groups as an illustration. Assuming the incidence rate of PGD-3 under iEPO treatment is 0.35 and acceptable margin of the equivalence is  $\pm 0.19$ , we will need 224 patients to have 80% power to detect an actual difference at 0.05 between two treatment group under this margin. This implies that the acceptable range of incidence rate for iNO treatment is from 0.21 to 0.59. Based on this estimate, we propose to enroll 200 lung transplant patients and 224 LVAD and heart transplant patients ( $n = 424$ ) over a period of 24 to 36 months; the exact time point for trial culmination between 24 and 36 months will be dependent on enrollment rate. There will be a 50% randomization rate for each inhaled agent such that 212 patients will receive iEPO and 212 patients will receive iNO.

**12. Data & Safety Monitoring:** The proposal is not introducing a new medication that has not been utilized by our group and safety has been established for this patient population through clinical practice and medication usage. Safety will, however, be determined by assessing reported, rare, adverse effects of iNO (systemic hypotension, methemoglobinemia, and rebound pulmonary hypertension after appropriate weaning) and iEPO (systemic hypotension, non-surgical bleeding related to thrombocytopenia, flushing, and rebound pulmonary hypertension after appropriate weaning) in order to accurately monitor adverse events (AE) during this study. The PI will review and sign off on AE's as they occur and perform a quarterly review and determine if AE's are related to the study or otherwise. AE's will be reported to the IRB per HRPP policies.

*Stopping Rule:* Subjects who meet the stopping criteria in section 4 continued to be enrolled and followed for primary outcome analysis. See section 4 for stopping criteria.

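### The analysis plan ignores the randomization strata, and its p<0.15 screen on treatment would almost never admit them, so any secondary analysis that pools operation types is conservative

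*Combined protocol and SAP*

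**What the plan says.** Table 1 (Study Summary) gives the sample size as "N = 424 (50/50 by randomization strata", with two populations: lung transplant, 200, and heart transplant or LVAD, 224. Section 4 refers only to "Using a 50% randomization process utilized and established by the CRU at Duke University Hospital". It names neither the stratification factor nor a block size.

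Section 4, Measured Outcomes, lists the shared clinical outcomes once: "Secondary endpoints related to clinical outcomes for all populations will be duration of postoperative mechanical ventilation, ICU Length of Stay (LOS), hospital LOS". It adds acute kidney injury and mortality in hospital and at 30 days, 90 days and 1 year.

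Section 11 is the only analysis plan. Its first step is "Univariate analysis will be performed to compare the difference of each variable between treatment groups by chi-square or Fisher exact tests", with t or Wilcoxon tests for continuous variables. Its second step screens non-outcome variables on association with treatment group at p<0.15, followed by stepwise selection, after which "we will determine the final set of covariates to be included in the final multivariable model to test the treatment group effect". Stratum, population and operation type are never named as model terms. A non-significant difference is taken to mean that the agents are equivalent. Nothing says whether the secondary outcomes are analysed across all 424 patients or within each population.

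**The concern.** A factor used to stratify the randomization belongs in the analysis if it predicts the outcome. Stratified allocation removes between-stratum variation from the treatment difference, but an unstratified test still counts that variation as noise. The test then rejects less often than its nominal level, and some power is thrown away.

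Ordinarily a covariate-adjusted model would put this right. Here it cannot, because the screen asks whether a variable is associated with treatment, not with outcome. Balance by design is exactly what makes a variable fail that screen, however strongly it predicts length of stay or death.

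The direction matters because section 11 treats non-significance as equivalence, so lost power favours the hoped-for conclusion. A pooled comparison with no stratum term or stratum-specific estimates would also hide any difference in effect between lung and heart/LVAD patients.

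**Working it through.** **1. Plan's own totals.** "we propose to enroll 200 lung transplant patients and 224 LVAD and heart transplant patients": 200 + 224 = 424. "212 patients will receive iEPO and 212 patients will receive iNO": 424/2 = 212. These agree. The lung share is w = 200/424 = 0.472, so w(1−w) = 0.249. The plan gives no power figure for secondary outcomes.

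**2. Can the stratum pass the screen?** Chi-square test of stratum by arm, no continuity correction, heart/LVAD held at 112/112:

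| Lung split | p |
|---|---|
| 100/100 | 1.0 |
| 104/96 | 0.68 |
| 114/86 | 0.149 (first below 0.15) |

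Block size is not documented, so two were assumed, with 2,000 simulated trials each. With blocks of 4 and full strata, p was always 1. With blocks of 6 and incomplete last blocks, the smallest p was 0.80. The stratum never passed. Under simple randomization it passed in about 15% of runs.

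**3. Mean and risk differences, pooled.** Let R² be the share of outcome variance explained by stratum (assumed) and k = 1/√(1−R²). The unadjusted standard error is too large by the factor k. Set the effect so that the usual unstratified formula gives 80% power, that is effect/SE = 1.96 + 0.842 = 2.802. Then:

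- actual type I error = 2[1 − Φ(1.96k)]
- unadjusted power = Φ[(2.802 − 1.96)k] = Φ(0.842k)
- adjusted power = Φ(2.802k − 1.96)

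| R² | k | Type I error | Unadjusted power | Adjusted power | Gain (points) |
|---|---|---|---|---|---|
| 0.10 | 1.054 | 3.9% | 81.3% | 84.0% | 2.7 |
| 0.15 | 1.085 | 3.4% | 81.9% | 86.0% | 4.0 |
| 0.25 | 1.155 | 2.4% | 83.4% | 89.9% | 6.4 |

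Gains are taken before rounding. Simulation with exact 1:1 allocation within strata of 200 and 224 (10,000 runs each) gave 81.3 v 83.8, 81.7 v 85.8 and 82.4 v 89.2. A 5-point gain needs R² of about 0.19.

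**4. What R² might be.** For a between-stratum difference of D within-stratum SDs, R² = 0.249D²/(1 + 0.249D²). For binary outcomes, R² = 0.249(difference in rates)²/[p(1−p)], with p the pooled rate. For example, rates of 10% and 30% give p = 0.206 and R² = 0.00997/0.1634 = 0.061. All inputs here are assumptions.

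| Assumed difference | R² | SE ratio | Type I error |
|---|---|---|---|
| 0.25 SD | 0.015 | 1.008 | 4.8% |
| 0.5 SD | 0.059 | 1.031 | 4.3% |
| 1.0 SD | 0.199 | 1.118 | 2.9% |
| 5% v 15% | 0.027 | 1.014 | 4.7% |
| 10% v 30% | 0.061 | 1.032 | 4.3% |
| 20% v 50% | 0.098 | 1.053 | 3.9% |

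**5. Logistic models.** With a within-stratum odds ratio of 1.8 and stratum rates of 10% and 30% (assumed), leaving out the stratum gives an odds ratio of 1.73. The standard error of the log odds ratio is 0.226 unadjusted and 0.235 adjusted, so it does not widen. The test statistic still falls, from 2.50 to 2.41.

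**The case against.** The strongest objection is that listing outcomes for all populations may only mean that they are measured in each one. Section 11 says the study was powered separately for the primary endpoints of each population, and those endpoints differ by operation. If secondary outcomes are also analysed by population, the lung v heart/LVAD stratum is constant and the problem disappears. This stands: pooling of the clinical secondary outcomes is not documented. But neither is separate analysis, and the purpose statement for Aim II does average cost over everyone randomized to a drug. The ambiguity needs settling either way.

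Three further readings are tempting, and the documents do not support them:

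- **That heart transplant v LVAD is a second omitted stratum.** Table 1 treats the 224 as one population, and nothing says the two operations were stratified separately. If they were not, omitting operation type costs precision only and leaves type I error near 5%.
- **That every standard error is too wide.** This is so for mean and risk differences. In the planned logistic models the odds ratio shrinks instead (step 5).
- **That adjustment lifts power from 80% to 84%, 86% or 90%.** Under stratified allocation the unadjusted test already sits a little above 80%, so the gains are smaller (step 3).

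It is also fair to say that the effect may be small, and that reading non-significance as equivalence is a separate and larger fault. Correcting that fault would remove much of the harm described here.

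**Conclusion.** The point holds in a conditional form. Section 11 omits the strata that Table 1 randomizes on, and its covariate screen would almost never let them in. Wherever operation types are pooled, unadjusted tests of mean and risk differences are conservative, and logistic odds ratios are pulled toward 1. Both lean toward a finding of no difference.

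The size depends on how far the populations differ. Type I error is 3.9% to 2.4% for R² of 0.10 to 0.25, with 2.7 to 6.4 points of power recoverable, but it is 4.3% or above when the populations differ by 0.5 SD or less. The figures assume 1:1 allocation within lung and heart/LVAD strata, as Table 1 implies; R² is not in the documents. No lung v heart/LVAD stratum issue arises for the operation-specific primary endpoints, or for any outcome analysed within one population. The change is worth making because it replaces a stated rule with a better one at almost no cost.

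**What to change.** In section 11:

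- State for each secondary outcome whether it is pooled or analysed by population.
- In every analysis that combines operation types, include the randomization stratum and operation type (lung, heart transplant, LVAD) as fixed terms, outside the p<0.15 screen and the stepwise selection.
- Alternatively, use a stratified method: a Mantel-Haenszel risk difference for kidney injury and mortality, and a stratum-adjusted linear model or van Elteren test for length of stay and ventilator hours.
- Report stratum-specific estimates beside any pooled one.

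Operation type is known for every patient, so the cost is a few sentences and one or two degrees of freedom.

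### ICU stay, hospital stay and ventilator hours are compared with no rule for patients who die first, so these three secondary results mix mortality with speed of recovery

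*Combined protocol and SAP*

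**What the plan says.** Section 4 (Measured Outcomes) lists the secondary endpoints for all populations as "duration of postoperative mechanical ventilation, ICU Length of Stay (LOS), hospital LOS, incidence of acute kidney injury, incidence of in-hospital mortality", followed by mortality at 30 days, 90 days and 1 year. Table 1 gives the stays in days and ventilation in hours. These are raw durations, not ICU-free or ventilator-free time.

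Section 11 has one rule for everything continuous:

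- Summary: "mean (standard deviation) for continuous variables for each arm".
- Unadjusted comparison: "t-tests or Wilcoxon Rank-Sum tests for continuous variables depending on data normality".
- Adjusted comparison: "generalized linear model for continuous outcomes".
- Interpretation: the results will show "if iNO is equivalent to iEPO (no significant difference) or significantly better or worse than iEPO".

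On the analysis set, it says that where patients change arm, "we will conduct the primary analysis based on the intent to treat (ITT) without reclassifying treatment assignment". That sentence deals with switching, not with death. I found no rule anywhere for a patient who dies in the ICU, in hospital or on the ventilator: no worst-rank score, free-days scale, competing-risk analysis or survivor-only set.

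**The concern.** A stay can end because the patient recovered or because the patient died. A t-test, rank test or linear model on the raw duration cannot tell the two apart. If deaths are simply entered as observed durations, an early death scores like a fast recovery. The plan expects deaths: it lists mortality at four time points in patients with end-stage heart or lung disease.

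The interpretation rule adds to the problem. Because a non-significant difference is read as equivalence, the distortion need not produce a false significant result to mislead. It is enough that deaths cancel a longer recovery among survivors. These three outcomes are part of the evidence for the trial's aim of showing a similar impact on clinical outcomes.

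**Working it through.** **Plan's own figure.** There is none to reproduce. The documents give no expected stay, standard deviation, death rate or power for these outcomes.

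**Inputs from the documents.** Section 11 gives 200 lung and 224 heart/LVAD patients with 1:1 allocation, so 100 and 112 per arm within population and 212 per arm if pooled.

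**Assumptions (not in the documents).** Survivors' stay is lognormal with mean 20 days and log-SD 0.7, identical in both arms. Deaths are entered at the observed duration. In-hospital mortality is 5% in one arm and 10% or 15% in the other. Time to death has mean 7, 20 or 40 days. Tests are two-sided at 0.05, so 2.5% in each direction.

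**Step 1: shift in the mean.** With survivor mean S, mean time to death D and mortality pL and pH, each arm's mean is (1 − p)·S + p·D. The higher-mortality arm minus the lower is therefore −(pH − pL)·(S − D).

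- 5% vs 15%, D = 7: −0.10 × (20 − 7) = −1.3 days.
- 5% vs 15%, D = 20: −0.10 × 0 = 0 days.
- 5% vs 15%, D = 40: −0.10 × (20 − 40) = +2.0 days.
- 5% vs 10%, D = 7: −0.05 × 13 = −0.65, about −0.7 days.
- Equal mortality with the same D in both arms: 0 days.

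The sign depends on whether deaths come before or after the survivors' typical duration. It can therefore differ among the three outcomes, since a given day of death may be early for hospital stay and late for ventilation.

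**Step 2: how often the planned Wilcoxon test misleads** (simulation, 1,500 to 3,000 trials per scenario).

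- 5% vs 15%, D = 7: it significantly favours the higher-mortality arm in about 12–16% of trials at 100–112 per arm, and in about 25% if pooled at 212 per arm.
- 5% vs 10%, D = 7: about 6–9% over the range of 100 to 212 per arm.
- 5% vs 15%, D = 20, 212 per arm: 2.2%, the nominal rate.
- 5% vs 15%, D = 40, 212 per arm: 0.3% favour the higher-mortality arm and 13% the lower-mortality arm, although survivors recover equally fast.

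**Step 3: masking.** At 5% vs 15% and D = 7, let survivors in the higher-mortality arm stay longer by a fraction x. The means are equal when 0.85 × 20(1 + x) + 0.15 × 7 = 0.95 × 20 + 0.05 × 7. That is 17(1 + x) + 1.05 = 19.35, so x = 18.30/17 − 1 = 7.6%. In simulation with survivor stays 10% longer and 212 per arm, the planned Wilcoxon is non-significant in about 95% of trials, which Section 11 would read as equivalence.

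**Step 4: would the separate mortality test reveal it?** Approximate power is Φ(|pH − pL|/SE − 1.96), with SE = √[(pL(1 − pL) + pH(1 − pH))/n].

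- 5% vs 15%: the numerator is 0.0475 + 0.1275 = 0.1750. SE is 0.0418 at n = 100, 0.0395 at 112 and 0.0287 at 212, giving power of about 67%, 72% and 94%.
- 5% vs 10%: the numerator is 0.0475 + 0.0900 = 0.1375. SE is 0.0371, 0.0350 and 0.0255, giving power of about 27%, 30% and 50%.

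**The case against.** The strongest reply has four parts.

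- **No primary endpoint is a duration.** The sample size does not rest on these outcomes. This stands and limits the severity.
- **Mortality is compared separately.** By Step 4, an imbalance large enough to distort the durations badly would often be significant in its own right. This stands in part. A 5-point imbalance would usually go undetected at 100–112 per arm, though the shift is then only about 0.7 days. Nor does a visible mortality difference correct the duration tests.
- **The plan does not say that deaths are entered as short stays.** Correct. A reader might infer from the tests named that every death counts at its observed duration. Section 11 neither says so nor excludes it. What can be said is that no rule is stated, and that applying the named tests directly to observed durations has the effects shown.
- **The direction is not fixed.** A reader might infer that the plan always flatters the arm with more deaths. The documents give no timing of deaths, and Steps 1 and 2 show no shift or the opposite one when deaths are later. A reader might also take the 25% figure as the trial's error rate, but it needs pooling at 212 per arm. Section 11 says the populations are powered individually, and the documents do not say that secondary outcomes are pooled.

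Late deaths do not rescue the method. The result is then distorted the other way, and it still does not measure recovery.

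**Conclusion.** The point holds as an unstated rule with real consequences. As written, the analysis of ICU stay, hospital stay and ventilator hours cannot separate mortality from speed of recovery, and Section 11's reading of non-significance as equivalence makes masking as harmful as a false difference. The omission itself is certain. Its size and direction are conditional on unequal mortality, on when deaths occur, and on the assumed stay distribution. Under those assumptions the distortion ranges from about −1.3 to +2.0 days at 5% versus 15% mortality, and is under a day at 5% versus 10% with early deaths. With equal mortality and similar timing of deaths it vanishes. Because these are secondary outcomes and mortality is tested separately, the change is advisable, at the lower end of that category. The documents do not support a claim that the primary comparison is affected.

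**What to change.** In Section 11, take these three outcomes out of the generic rule for continuous variables. Name as their analysis the time to ICU discharge alive, to hospital discharge alive and to extubation alive, each with death before that event as a competing event. Compare the arms on the cumulative incidence of the event. Show days and hours among survivors descriptively only, and report in-hospital mortality by arm beside each result.

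Also state how an LVAD patient who is transplanted during the index stay is handled. Section 6 (Subject Identification, Recruitment, & Compensation) ends that patient's LVAD-group data at transplant, so the stay has no ordinary discharge.

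The cost is a change of wording in the analysis section, with no change to sample size, visits or care. The documents do not list the date fields collected, but durations and in-hospital mortality cannot be computed without the dates of discharge, extubation and death. The downside is an effect measure less direct than a difference in mean days. The rule should be fixed before outcomes are seen by arm, so that the handling of deaths cannot be chosen from the data.

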### Data Collection

*Secondary measures will be hemodynamic variables* (similar to those measured in Table 2) such as transesophageal echocardiographic (TEE) evaluation of RV function based on stand-of-practice protocol, intravenous administration of inotropes, serial measures of postoperative serum creatinine and GFR, resolution of elevated liver function tests (heart failure patients, illustrates improvement in RV function), incidence of thrombocytopenia (platelet count < 150 x 10^9/L) and trajectory of resolution, as well as ventilation-to-perfusion matching (arterial oxygen tension, PaO2; arterial carbon dioxide tension, PaCO2; and fraction of inspired oxygen, FiO2). Variables will be recorded at designated time points during the entire duration of administration – from initiation in the operating room to cessation in the ICU. These time points include: Intraoperative before surgical incision, time = 0 (initiation of PVD), 30 minutes, 2 hours, 6 hours, 12 hours, 18 hours, 24 hours, and every 6 hours up through 72 hours after initiation. These secondary measures will be obtained up through 72 hours after initiation regardless of cessation or continuation of the inhaled PVD. After 72 hours, increments of every 12 hours thereafter will be assessed if PVD administration continues. Ventilation and perfusion nuclear scans will be obtained and recorded per standard clinical practice for each group of lung transplant recipients. Established protocols with criteria for initiation of medication weaning have been created according to each medication based on individual pharmacokinetic properties. Once established criteria are met, weaning of each inhaled PVD will begin and continue until the medication is terminated according to standardized weaning protocols established for lung transplant patients and heart transplant/LVAD patients.

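### Covariates are chosen for chance association with the randomised treatment, so most of the power that planned adjustment could give is lost

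*Combined protocol and SAP*

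**What the plan says.** Section 11 first compares the arms on each variable by univariate tests, so an unadjusted outcome comparison is reported. It then sets the covariate rule: "All non-outcome variables meeting" p < 0.15 "association with treatment group will be considered for variable selection to build a multivariable regression model". The regression for each outcome ("logistic regression for binary outcomes or generalized linear model for continuous outcomes") starts with the variables that pass. The next step reads: "Based on stepwise variable selection, we will determine the final set of covariates to be included in the final multivariable model". That final model tests treatment, and a non-significant result is taken to mean that the agents are equivalent.

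No section names a covariate that must be in the model, and none screens on association with outcome. The stepwise entry and removal levels are not stated. Table 1 gives a 1:1 split by randomisation strata but does not say that strata enter the model.

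Three other places bear on the point:
- The sample-size paragraph of Section 11: "Assuming the incidence rate of PGD-3 under iEPO treatment is 0.35 and acceptable margin of the equivalence is" ±0.19, with 200 lung patients.
- Section 4, Measured Outcomes: "Secondary endpoints related to clinical outcomes for all populations will be duration of postoperative mechanical ventilation", with length of stay among the others.
- Data Collection: "Secondary measures will be hemodynamic variables". Their schedule begins before treatment: "These time points include: Intraoperative before surgical incision, time = 0 (initiation of PVD".

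**The concern.** Adjustment gains power when a covariate predicts the outcome. Under randomisation its association with treatment is noise, so a screen on that association selects on the wrong relation. The variables most worth adjusting for are left out of most trials, and which ones enter depends on chance imbalance and then on an unspecified stepwise procedure.

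Lost power matters more than usual here, because failing to find a difference is read as equivalence. The model behind the main test is also unknown until the data are in, which is hard to defend when a fixed list would cost only text.

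**Working it through.** **1. The plan's own figure.** Section 11 gives N = 224 for 80% power (iEPO rate 0.35, margin 0.19, true difference 0.05). The usual formula at one-sided 0.05, with iNO at 0.40, gives per arm (1.645 + 0.842)² × (0.35×0.65 + 0.40×0.60) / (0.19 − 0.05)² = 148, or 296 in total. The stated 224 is not reproduced. That is a separate matter; nothing below depends on it.

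**2. Retention.** For a randomised baseline variable the probability of passing p < 0.15 is 0.15, whatever its prognostic value. Stepwise selection can only remove it afterwards. The chance that three independent prognostic variables all pass is 0.15³ = 0.3%.

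**3. Binary outcome, lung, 100 per arm.** From the plan: rate 0.35, and a true difference equal to the margin (0.35 vs 0.54). Assumed: independent standard-normal covariates; t-test screen at 0.15, then backward elimination at Wald p < 0.05; two-sided 0.05 Wald test of the treatment log-odds ratio. There were 10,000 trials per cell (Monte Carlo SE about 0.4 points at 20%, 0.2 at 5%).

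| One covariate, log-OR per SD | 0.5 | 0.8 | 1.2 |
|---|---|---|---|
| Kept by the plan's rule | 13% | 15% | 15% |
| Non-significant: unadjusted | 22% | 21% | 21% |
| Non-significant: plan | 21% | 20% | 18% |
| Non-significant: fixed adjustment | 21% | 18% | 13% |
| Mean SE of log-OR: plan | 0.294 | 0.296 | 0.299 |
| Mean SE of log-OR: fixed | 0.303 | 0.316 | 0.340 |
| Type I error (0.35 vs 0.35): plan | 4.7% | 4.1% | 3.8% |
| Type I error: fixed | 4.8% | 4.7% | 5.0% |

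On the log-odds scale fixed adjustment does not narrow the interval; it raises power because the adjusted estimate moves further from zero than its SE grows. At a true risk difference of 0.05 the mean estimate was 0.049 to 0.052 for every method, so there is no bias.

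With five covariates at log-OR 0.3 / 0.5 each, the plan keeps on average 0.36 / 0.60 of the five. Non-significance is 22% / 20% (plan) against 19% / 14% (fixed).

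**4. Share of the gain lost.** A second simulation (20,000 trials per scenario, N = 200, one covariate with odds ratio 2.72 per SD) gave power of 78.9% unadjusted, 80.6% under the plan and 84.7% with fixed adjustment. The share lost is (84.7 − 80.6) / (84.7 − 78.9) = about 70%. Across all binary, continuous and equivalence-test scenarios tried, it was 61% to 85%. It can fall below 85% because the screen picks out the trials with the largest imbalance, where adjustment helps most.

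**5. Continuous secondary outcomes, 100 per arm.** With unit SD the unadjusted SE is √(2/100) = 0.141; fixed adjustment multiplies it by about √(1 − R²). Simulation used 20,000 trials per cell and normal errors.

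| Assumed R² | 0.1 | 0.2 | 0.3 |
|---|---|---|---|
| Mean SE: plan | 0.140 | 0.139 | 0.138 |
| Mean SE: fixed | 0.134 | 0.127 | 0.119 |
| Narrower by | 4% | 9% | 14% |
| 0.4 SD difference missed: plan | 18.6% | 17.4% | 16.5% |
| 0.4 SD difference missed: fixed | 15.8% | 11.9% | 8.1% |

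Unadjusted, 19.5% to 19.9% are missed.

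**6. If equivalence were judged on a marginal risk difference against 0.19**, an analysis Section 11 does not specify, power at a true 0.05 would be 63% / 64% / 65% (plan) against 66% / 69% / 74% (fixed) for the three single-covariate strengths.

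**7. Strata, conditionally.** If the strata are the two populations and splits are exact (100+100 lung, 112+112 heart/LVAD), chi-square is 0 and p = 1, so stratum never passes. If an outcome is then analysed across populations whose means differ by d SD, omitting stratum multiplies the SE by √(1 + (200/424)(224/424)d²). For assumed d = 0.25 / 0.5 / 1.0 this is an increase of 0.8% / 3% / 12%.

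**The case against.** The strongest reply is that nothing invalid results. An unadjusted comparison of randomised arms is valid and is reported, the plan's rule matches or slightly beats it, and type I error under the plan stays at or below 5%. The sample size assumes no covariates, so the missing power was never promised. All of this stands; the point is forgone power and not bias.

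The size can also be challenged. The documents give no covariate strengths, and a single weak covariate (log-OR 0.5) gives essentially no gain. Five covariates at 0.5 have a combined SD of √5 × 0.5 = 1.12 on the logit scale, nearly the strongest single case. In that cell fixed adjustment had a type I error of 5.9% against 4.7% for the plan, so part of its 6 points is a more liberal test. A larger run (30,000 null and 15,000 alternative trials) gave 5.3% against 4.5%, and at equal size 15.3% missed against 19.7%, about 4.4 points. These corrections are fair and limit the size, not the mechanism. Ventilator hours and length of stay may be skewed, so the normal-error figures for them are indicative.

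Finally, the strata figures need exact balance and a cross-population analysis, neither of which is stated, and the post-initiation measures are probably meant as outcomes. Both points are therefore only conditional.

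**Conclusion.** The concern holds. The rule keeps a prognostic baseline variable at most about 15% of the time and forgoes most of the power from adjustment. For the lung endpoint at a true difference equal to the margin, that is 0 to 6 percentage points more misses than fixed adjustment, with the upper end nearer 4 to 5 at equal type I error. For continuous outcomes the intervals could be 4% to 14% narrower.

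Most of the 18% to 22% chance of wrongly reading equivalence comes from treating non-significance as equivalence, a separate fault.

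Confidence is high on the rule itself and moderate on the size, which rests on assumed covariate strengths and an assumed stepwise threshold. It is low on two conditional points:
- The screened variables are not expressly limited to baseline. If post-initiation measures were included, the screen would favour variables that treatment changes, and adjusting for them could distort the effect in either direction.
- Stratum or procedure matters only where populations are analysed together. Heart transplant and LVAD have different primary endpoints.

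No figure is claimed for post-initiation variables or for procedure within heart/LVAD. The point should be fixed; it does not invalidate the trial.

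**What to change.** In Section 11:
- Delete the p < 0.15 screen and the stepwise step.
- For each endpoint, pre-specify one model with treatment and a short fixed list of baseline variables, chosen for expected relation to the outcome and recorded before the inhaled agent is started. The pre-incision values already scheduled under Data Collection are candidates.
- Add stratum or procedure wherever populations or procedures are analysed together.
- State that nothing measured after initiation is a covariate, and include the pre-incision value in the repeated-measures models.
- Report the marginal risk difference with its confidence interval, which is the scale of the margin, beside the unadjusted result.

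The cost is SAP text, with three cautions. The list must be short where events are few: the 5.9% type I error above arose with five covariates and about 70 events (0.35 × 200), and the documents give no RVAD event rate. The list must be fixed and dated by people who have not seen outcomes by arm, because unblinding occurs at ICU discharge (Section 4) and the principal investigator and statisticians have data access (Section 13). Baseline variables other than procedure and the pre-incision values are not itemised, so someone must check that they are recorded.
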